#### Quantifying between-study heterogeneity

An indication for the heterogeneity among estimates from different study sites will be obtained by calculating  $I^2$  according to Higgins et al (4). The  $I^2$  statistic is to be interpreted as the proportion of total variation in the estimates of treatment effect that is due to heterogeneity between studies. Low, moderate and high levels of heterogeneity correspond to  $I^2$  values of 25%, 50% and 75%

respectively. In case I is high, it is worthwhile to explore sources of heterogeneity (Section 3.4.5).

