## Strategy for data synthesis

#### Inclusion criteria

We will pool seasonal IVE estimates from the individual study sites in line with the objectives as per study protocol (Section 3.1). Estimates that are not obtained following the study protocols will not be retained for the primary meta-analysis, but might be considered for inclusion as part of a sensitivity analysis (Section 3.4.6). Whenever there are two or more site-specific estimates retained, a meta-analysis will be performed.

as per study protocol) might be considered upon lack of heterogeneity (see Sections 3.4.4 and 3.4.5).

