#### Exploring sources of heterogeneity

In case of at least 5 site-specific IVE estimates, stratified analyses and meta-regression might be used to explore whether the magnitude of the IVE estimates are associated with design or other characteristics of the study site-specific estimates of interest (e.g. study design, adjustments for certain covariates). In stratified analyses, the meta-analysis (as in Section 3.3.3) will be repeated for each stratum of characteristics separately. In meta-regression, the meta-analysis (as in Section 3.3.3) will be extended with the site-specific study characteristics as predictor variables and relative risk ratios (RRRs) will be obtained (5). For example, assume the characteristic of interest is study design (cohort vs case-control studies). Then, the RRRs is to be interpreted as the ratio of the pooled IVE estimate of the case-control studies to the pooled IVE estimate of the cohort studies.

The permutation test as proposed by Higgins et al (6) will be used to assess the significance of a study characteristic while controlling the risk of false-positive results. If the study characteristic is not statistically significant in the meta-regression model, the study characteristic is unlikely a source of heterogeneity, and pooling across that study characteristic might be considered.

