#### **Presentation of results**

The site-specific IVE estimates (and 95% CIs) will be presented using a forest plot complemented with the pooled IVE estimate (and 95% CIs) as outlined in the report template. Estimates that were excluded from meta-analysis will included in the forest plot, but these estimates will be tagged as excluded. An example of a forest plot with pooled estimates by setting is given in Figure 1. This plot is generated using artificial data based on cohort designs.

Vaccinated Unvaccinated

	Vaccina	alcu	Uliva	comateu		
Study	Ν	n	Ν	n		Vaccine effectiveness % [95% CI]
Primary care FOR ILLUSTRATION ONLY: ARTIFICIAL DATA					ION ONLY: ARTIFICIAL DATA	
Country E	650	23	450	32		└───── ── 50.2 [ 16.1, 70.5]
Country D(3)*	1000	63	1000	70	μ	– 10.0 [-25.0, 35.2]
Country D(2)	3000	63	4000	280		→ 70.0 [ 60.7, 77.1]
Country D(1)	2500	61	2800	196		⊢■ 65.1 [ 53.8, 73.7]
Country C	500	21	500	35	H	40.0 [ -1.6, 64.6]
Country B	250	7	500	35		⊢−−−−− 60.0 [ 11.2, 82.0]
Country A	1200	42	1400	98		— 50.0 [ 28.8, 64.9]
Weighted average					52.49 [35.37, 65.07]	
(Heterogeneity	: 12 =77.19	%)				
Hospital						
Country F	1200	17	2400	168		⊢−−− 79.8 [ 66.8, 87.7]
Country E	400	7	500	35		→→→ 75.0 [ 44.3, 88.8]
Country A	800	17	780	55		▶ ● 69.9 [ 48.5, 82.3]
Weighted average					75.57 [66.01, 82.45]	
(Heterogeneity: 12 =0%)						
* excluded from pooled estimate because outlying and influential						
				Г 		
				-50	-12.5	25 62.5 100
Vaccine effectiveness %				ccine effectiveness %		

Figure 1: Forest plot and meta-analyses of influenza vaccine effectiveness, by health care setting. This plot is generated using artificial data based on cohort designs

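### A low or moderate I² point estimate is weak evidence for the lack of heterogeneity that SAP 3.4.1 uses to allow wider pooling

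*Combined protocol and SAP*

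**What the plan says.** The generic SAP (Annex 4) covers this in four places.

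- **3.4.4, Quantifying between-study heterogeneity.** "An indication for the heterogeneity among estimates from different study sites will be obtained by" calculating I². "Low, moderate and high levels of heterogeneity correspond to" 25%, 50% and 75%. When I² is high, "it is worthwhile to explore sources of heterogeneity (Section 3.4.5"). The SAP names no Q test, confidence interval for I², tau or prediction interval, and gives no other prompt to look for sources.
- **3.4.1, Inclusion criteria.** A meta-analysis is run from two retained estimates upward. Some wider pooling "might be considered upon lack of heterogeneity (see Sections 3.4.4 and 3.4.5"). The start of that sentence is missing from the text available to us, so its exact scope is unknown.
- **3.4.5, Exploring sources of heterogeneity.** "In case of at least 5 site-specific IVE estimates, stratified analyses and meta-regression might be used". Significance is judged by a permutation test. "If the study characteristic is not statistically significant in the meta-regression model, the study characteristic is unlikely a source of heterogeneity". On that basis the SAP lets estimates be combined over the characteristic in question.
- **3.4.7, Presentation of results.** The example forest plot, on artificial cohort data, pools primary care and hospital separately.

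The SAP Background prefers a random-effects model because true effects may differ between sites.

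**The concern.** I² depends on how precise the sites are as well as on how far their true effects differ. With few or imprecise estimates, a low or moderate I² says little about whether VE is the same across settings or designs. Brand-specific VE is the primary objective, and its site estimates are less precise than those for overall VE. Yet the SAP attaches its only stated prompt to a high value and cites lack of heterogeneity as a reason to pool more widely. A setting- or design-averaged VE could then be reported, with heterogeneity called low or moderate, although the strata differ and nothing in the output warns of it.

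**Working it through.** **1. The plan's own figures.** Inverse-variance random-effects meta-analysis (REML) of the log RR from the SAP Figure 1 counts gives primary care VE 52.49% (35.37 to 65.07), I² 77.1%, and hospital VE 75.57% (66.01 to 82.45), I² 0%. Both match the printed values. The primary care match needs all seven rows, including Country D(3), although its footnote reads "excluded from pooled estimate because outlying and influential". This is an inconsistency in an artificial example only.

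**2. What I² ≥ 75% requires.** With I² = (Q − (k−1))/Q, I² ≥ 0.75 means Q ≥ 4(k−1). The null p is P(χ² on k−1 df > 4(k−1)):

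| k | Q needed | null p |
|---|---|---|
| 2 | 4 | 0.046 |
| 3 | 8 | 0.018 |
| 5 | 16 | 0.003 |
| 10 | 36 | 0.00004 |

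**3. Site standard errors.** Inputs from Annex 3: 500 cases, 1:1 controls, true VE 50%. At 50% coverage its cell-count formula gives a = 207.1, b = 292.9, c = 292.9, d = 207.1. Then SE(log OR) = √(1/a + 1/b + 1/c + 1/d) = 0.128, and the lower limit is 1 − 0.5·exp(1.96 × 0.128) = 35.7%. At 20% coverage the SE is 0.163 and the lower limit 31.2%. Both agree with the plan's statement of more than 30%. For a brand with a 40% share, other brands excluded as in Annex 3, a and b are multiplied by 0.4. The SE is then 0.170 at 50% coverage and 0.243 at 20%.

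**4. Chance that I² stays below 75%.** Assumed: true VE 50% in three sites and 70% in three, equal SEs, no heterogeneity within setting. δ = ln(0.50/0.30) = 0.511. Q is noncentral χ² on 5 df with noncentrality (3 × 3/6)(δ/SE)². A miss is Q < 20.

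| SE | noncentrality | miss |
|---|---|---|
| 0.128 | 23.9 | 20% |
| 0.17 | 13.5 | 62% |
| 0.23 | 7.4 | 88% |

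Simulation at SE 0.17 with within-setting tau 0.3 on the log OR scale gives a miss rate of 26%.

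**5. Few estimates.** Assumed tau 0.3 (95% of true site VEs between about 10% and 72% around 50%) and SE 0.165 to 0.30. Q is χ² on k−1 df multiplied by (SE² + tau²)/SE², and I² < 25% means Q < (k−1)/0.75. The probability of I² below 25% is 42–59% at k = 2 and 18–43% at k = 4.

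**6. The permutation test at its minimum.** Five estimates split 2:3 allow 10 allocations, so the smallest two-sided p is 1/10 = 0.10. Six split 3:3 allow 20, and each allocation has a mirror image, so it is 2/20 = 0.10. The SAP states no alpha. At an assumed 0.05 a two-level characteristic with these splits can never be significant. A 3:4 split can reach 1/35 = 0.029.

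**7. Illustration on the Figure 1 counts (DerSimonian–Laird).** With D(3) removed as footnoted, primary care VE is 59.3% and hospital VE 75.6%, z = 2.50, p = 0.012. Over the nine estimates Q = 16.71, so I² = (16.71 − 8)/16.71 = 52.1%, below the benchmark. The test-based 95% CI for I² is 0 to 77.5%. Pooling all nine would give 64.0% (55.2 to 71.0). With D(3) kept, I² over ten estimates is 78.9% and the prompt would apply.

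**The case against.** A reader might infer three stronger things, and the documents support none of them.

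- **That I² alone decides.** Section 3.4.4 calls I² an indication and does not forbid exploration at lower values. The entry condition in 3.4.5 is the number of estimates, not I². Section 3.4.1 cites both sections, so with two to four estimates it can equally be read as making wider pooling unavailable.
- **That real differences are usually missed.** This depends on the assumed difference, precision and within-setting spread, as step 4 shows. With VE 60% against 30%, five to ten sites of 500 cases and coverage of 20–50%, I² reaches 75% in 46–90% of simulated runs.
- **That sites are pooled as if homogeneous.** The model is random-effects, the forest plot shows every site, and the example already pools by setting. The 64.0% in step 7 is constructed here; the SAP prints no such pool.

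Two further points are fair. The Figure 1 illustration is artificial and depends on removing D(3). A direct setting contrast is also no cure for low power. In the step 4 scenario at SE 0.17 it has 96% power with known variances, 78% as a two-sample t contrast, and 29% as a t contrast with tau 0.3. This argues for reporting the contrast with its interval and against reading its non-significance as equality.

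What stands against the plan is that no uncertainty is attached to I², that a high value is the only stated prompt, and that lack of heterogeneity or a non-significant test is read as grounds for pooling. That the SAP is guidance, to be updated after the pilot, makes the change easier but does not remove the need for it.

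**Conclusion.** The point holds in limited form. The I² value is the only heterogeneity measure specified, and the 75% benchmark is a test whose null p falls from 0.046 to 0.00004 between two and ten estimates. A low or moderate value is weak evidence that VE is the same across sites. The miss rates of 20% to 88% are conditional on an assumed 50% against 70% split over six equal sites, and within-setting heterogeneity changes them. The permutation test does not make up for this with five or six evenly split estimates, assuming alpha 0.05. The consequence is a setting- or design-averaged VE without adequate warning. It does not amount to an assumption of homogeneity, nor does it show that differences will usually go unseen.

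**What to change.** - **3.4.4.** For every meta-analysis, report tau on the log scale, I² with a 95% CI and, for three or more estimates, a 95% prediction interval for VE. State that lack of heterogeneity is not concluded from the value of I² or from a non-significant test. Remove a high I² as the condition for exploration.
- **3.4.5.** Estimate the setting and study-design contrasts, as ratios of ORs or RRs with 95% CIs, whatever I² is, whenever each stratum has an estimate. Bring the sentence on non-significance and the lack-of-heterogeneity condition in 3.4.1 into line.
- **3.4.7.** Confirm the by-setting presentation already shown in the example plot. Any value pooled across strata is secondary and shown beside the stratum estimates.

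The cost is SAP wording and a few lines of standard meta-analysis output, with no new data. The downside is wide intervals when sites are few, and stratum estimates that are less precise than one pooled figure.

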#### Exploring sources of heterogeneity

In case of at least 5 site-specific IVE estimates, stratified analyses and meta-regression might be used to explore whether the magnitude of the IVE estimates are associated with design or other characteristics of the study site-specific estimates of interest (e.g. study design, adjustments for certain covariates). In stratified analyses, the meta-analysis (as in Section 3.3.3) will be repeated for each stratum of characteristics separately. In meta-regression, the meta-analysis (as in Section 3.3.3) will be extended with the site-specific study characteristics as predictor variables and relative risk ratios (RRRs) will be obtained (5). For example, assume the characteristic of interest is study design (cohort vs case-control studies). Then, the RRRs is to be interpreted as the ratio of the pooled IVE estimate of the case-control studies to the pooled IVE estimate of the cohort studies.

The permutation test as proposed by Higgins et al (6) will be used to assess the significance of a study characteristic while controlling the risk of false-positive results. If the study characteristic is not statistically significant in the meta-regression model, the study characteristic is unlikely a source of heterogeneity, and pooling across that study characteristic might be considered.

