#### LIST OF ABBREVIATIONS

- AD-MA Aggregated data meta-analysis
- CI Confidence interval
- DRIVE Development of Robust and Innovative Vaccine Effectiveness
- IPD-MA individual participant data meta-analysis
- IVE Influenza vaccine effectiveness
- OR Odds ratio
- RR Relative risk
- SAP Statistical Analysis Plan
- RRR Relative Risk Ratio

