#### **Meta-analysis**

For every objective listed in Section 3.1, a meta-analysis will be performed. First, the study sitespecific IVE estimates will be back-transformed to the original relative risk (RR) estimates (in case of cohort studies) and odds ratio (OR) estimates (in case of case-control studies), which will be subsequently log-transformed, or

 $\log RR \text{ or } \log RR = \log(1-VE)$ 

Then, standard inverse variance weighted random-effects meta-analysis of the log-transformed RR and OR estimates will be used to obtain the pooled estimate (2). The pooled estimate (and 95% CI) will then be back-transformed to obtain the pooled IVE estimate (and 95% CI), expressed in %.

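### SAP 3.4.5 reads the meta-regression RRR as a ratio of pooled IVEs, but it is a ratio of (1−IVE); read literally, the direction reverses when both IVEs are positive and unequal

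*Combined protocol and SAP*

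**What the plan says.** All references are to the generic SAP in Annex 4 of the combined document.

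- Section 3.4.2 (Meta-analysis) turns each site's IVE back into an RR (cohort) or OR (case-control) and takes logs, giving log(1−VE). Then "standard inverse variance weighted random-effects meta-analysis of the log-transformed RR and OR estimates will be used to obtain the pooled estimate". Only the result of that pooling returns to the IVE scale: it "will then be back-transformed to obtain the pooled IVE estimate (and 95% CI), expressed in" per cent.
- Section 3.4.5 (Exploring sources of heterogeneity) offers stratified analyses and meta-regression as options when at least five site estimates are available. In meta-regression, the same meta-analysis "will be extended with the site-specific study characteristics as predictor variables and relative risk ratios (RRRs) will be obtained (5"). The abbreviation list expands RRR as "Relative Risk Ratio".
- Section 3.4.5 then takes study design as its example and says that the RRR "is to be interpreted as the ratio of the pooled IVE estimate of the case-control studies" to that of the cohort studies.

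**The concern.** The last statement does not follow from the model. A coefficient estimated on log(1−VE) becomes, after exponentiation, a ratio of (1−IVE) values. A higher IVE means a smaller (1−IVE), so an RRR below 1 means that the numerator group has the higher effectiveness. The SAP sentence tells the reader that it has the lower.

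The sentence is the SAP's only instruction on how to read an RRR, and the document exists to guide the writing of pooled-analysis SAPs. Study design and covariate adjustment are the characteristics it names for examination. A report that followed the sentence could say that the design or adjustment with the higher IVE has the lower one. It would also attach to the IVE ratio a confidence interval that belongs to a different quantity.

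**Working it through.** **1. What the coefficient is.** Take the section 3.4.2 model with a binary characteristic x (1 = case-control, 0 = cohort):

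log(1−VE_i) = β0 + β1·x_i + random site effect + sampling error.

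Then exp(β0) = 1−IVE_cohort and exp(β0+β1) = 1−IVE_cc, so

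RRR = exp(β1) = (1−IVE_cc)/(1−IVE_cohort).

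The SAP sentence equates this with IVE_cc/IVE_cohort. Section 3.4.2 provides a back-transformation for the pooled estimate only; none is given for β1.

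**2. When the direction reverses.** Write A for the numerator IVE and B for the denominator IVE.

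- If A > B > 0, then 1−A < 1−B. So RRR < 1 while A/B > 1. Swapping A and B reverses both inequalities. Hence the two ratios are on opposite sides of 1 whenever both IVEs are positive and unequal. A grid of IVEs from 1% to 99% confirmed this for every unequal pair.
- If A = B (not zero), both ratios are 1.
- Both negative, −10% and −20%: RRR = 1.10/1.20 = 0.917 and IVE ratio = 0.50, on the same side of 1.
- Mixed signs, −10% and 30%: RRR = 1.10/0.70 = 1.571 and IVE ratio = −0.33, which has no useful meaning.

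**3. Reproducing the SAP's own figure.** The documents state no RRR. The only worked figure is the forest plot in section 3.4.7, on artificial cohort data, with pooled IVE by setting. The site inputs are log RR = log[(n1/N1)/(n0/N0)], with variance 1/n1 − 1/N1 + 1/n0 − 1/N0, pooled by inverse-variance random effects.

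- Primary care, all seven rows: REML gives 52.49% (35.37 to 65.07), I² 77.1%, exactly as printed. DerSimonian-Laird gives 52.43% (33.70 to 65.87), I² 80.4%.
- Hospital, three rows: 75.57% (66.01 to 82.45), I² 0%, exactly as printed.
- The printed primary-care value is obtained only with the Country D(3) row included, although the footnote marks that row as left out of pooling. Without it, REML gives 59.12% (48.29 to 67.68).

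**4. RRR against IVE ratio.**

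| Comparison (numerator vs denominator) | RRR | IVE ratio |
|---|---|---|
| Hypothetical, 60% vs 40% | 0.40/0.60 = 0.67 | 60/40 = 1.50 |
| Hospital vs primary care, as printed | 0.2443/0.4751 = 0.51 | 75.57/52.49 = 1.44 |
| Hospital vs primary care, tagged row left out | 0.2443/0.4088 = 0.60 | 75.57/59.12 = 1.28 |

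Read as the SAP instructs, 0.514 would imply a hospital IVE of 0.514 × 52.49% = 27.0%. The printed value is 75.57%.

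**5. Fitted meta-regression.** REML on the same rows with a hospital indicator gives RRR 0.520 (0.292 to 0.925) with all seven primary-care rows, and 0.604 (0.384 to 0.949) without the tagged row. These differ slightly from step 4 because one between-site variance is shared by both settings. Both lie below 1 although hospital has the higher IVE.

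**The case against.** The strongest reply is that the sentence does little harm. It is an example inside an optional, exploratory step of a template that is to be updated after the pilot season and still contains bracketed placeholders. The quantity is correctly named a relative risk ratio, and section 3.4.2 states the scale. If stratified results are shown next to the RRR, a reversed reading would clash with them visibly. The numerical example is also weak: it is artificial, has no case-control studies, and its printed primary-care average conflicts with its own footnote.

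Most of this stands, and it limits the severity. It does not make the sentence right. Nor can the term be excused as loose wording for RR or OR, because section 3.4.2 uses pooled IVE estimate for the quantity obtained after back-transformation. The direction result is algebra and does not depend on the example; only the quoted sizes do.

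A reader might infer more: that every comparison reported under the SAP would be reversed, or that decisions on pooling would be corrupted. The documents do not support either.

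- Site-specific, pooled and stratified IVEs never pass through the RRR and stay correct.
- Section 3.4.5 lets pooling across a characteristic be considered when that characteristic is not significant, judged by a permutation test. That test gives the same answer however the RRR is described.
- Reversal is not guaranteed when a pooled IVE is zero or negative.

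Whether the report template repeats the error cannot be judged, because it is not among the documents.

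**Conclusion.** The interpretation sentence in SAP 3.4.5 is wrong for the model the SAP specifies. Read literally, it reverses the direction and misstates the size of a meta-regression RRR whenever both pooled IVEs are positive and unequal. In the SAP's own illustration the gap is 0.51 against 1.44, or about 0.60 against 1.28 without the tagged row.

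This rests on two assumptions. First, the meta-regression extends the log-scale model of section 3.4.2. The text points to a Section 3.3.3 that is absent from the table of contents, but 3.4.2 holds the only meta-analysis model described. Second, the RRR is the exponentiated coefficient, as its name implies.

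It is a should-fix, not a critical flaw: the analysis is optional and exploratory, and the primary brand-specific, type-specific and overall IVE estimates are untouched.

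**What to change.** Replace the sentence in section 3.4.5 with: *The RRR is the ratio of the pooled OR of the case-control studies to the pooled RR of the cohort studies, i.e. (1−IVE_cc)/(1−IVE_cohort); an RRR below 1 means higher IVE in the case-control studies.* Wherever an RRR is reported, show the back-transformed IVE and its 95% CI for each group beside it, so that the direction can be checked at sight.

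The cost is one sentence and two figures per reported RRR that the same model or the stratified analyses already supply. No estimate, test or pooling decision changes, and there is no statistical downside.

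### The pooled-analysis SAP reads a non-significant permutation test as evidence that a characteristic does not drive heterogeneity; with 5 or 6 estimates and a two-level characteristic, the test cannot reach two-sided 0.05

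*Combined protocol and SAP*

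**What the plan says.** Annex 4, section 3.4.5 (Exploring sources of heterogeneity), sets the entry condition: "In case of at least 5 site-specific IVE estimates, stratified analyses and meta-regression might be used". Its worked example is a two-level characteristic: "assume the characteristic of interest is study design (cohort vs case-control studies"). A permutation test "will be used to assess the significance of a study characteristic while controlling the risk of false-positive results". The consequence of a non-significant result is stated without qualification: "If the study characteristic is not statistically significant in the meta-regression model, the study characteristic is unlikely a source of heterogeneity". The same sentence goes on to say that pooling across the characteristic may then be considered.

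Section 3.4.1 (Inclusion criteria) refers back to this step. In the available text its last sentence begins mid-clause, so its subject is lost, but it says that something "might be considered upon lack of heterogeneity (see Sections 3.4.4 and 3.4.5"). Section 3.4.4 is the I² section. It labels 25%, 50% and 75% as low, moderate and high, and suggests exploring sources when I² is high. It gives no I² value above or below which estimates may be pooled across a characteristic.

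For the permutation test the SAP gives no significance level, no sidedness, no minimum number of estimates per level, and no caution about small numbers of sites.

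**The concern.** There are two separate problems.

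The first is logical. A non-significant test means the data did not show a difference. It does not mean that a difference is unlikely. With few sites, low power is the usual reason for non-significance.

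The second is specific to this test. A permutation p-value is a count of relabellings divided by the number of possible relabellings. With few sites and two levels there are few distinct relabellings, so the p-value has a floor that no effect size can get below. If the floor lies above the significance level, the test has only one possible result, and under section 3.4.5 that result leaves pooling permitted.

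What is at stake is the reading of pooled brand-specific effectiveness, the protocol's primary objective. A figure that mixes settings or designs with different true effectiveness could be reported with a statement that the characteristic probably does not matter, on the strength of a test that could not have said otherwise.

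**Working it through.** **Inputs.** From section 3.4.5: a minimum of five estimates, a permutation test, and a two-level characteristic as the example. From section 3.4.2: inverse-variance random-effects analysis of log RR or log OR. Assumed: significance level 0.05, two-sided, in line with the 95% intervals the SAP uses throughout. The documents state no attainable p-value or power for this test, so there is no figure of theirs to reproduce.

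**Floor of the p-value.** With n estimates, m of them in one level, there are C(n, m) distinct labellings. Taking the two-sided p as the share of labellings whose absolute statistic is at least the observed one:

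- unequal split: minimum p = 1 / C(n, m)
- even split: minimum p = 2 / C(n, n/2), because swapping the two labels gives the same absolute statistic

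| Estimates | Split | Labellings | Minimum two-sided p |
|---|---|---|---|
| 5 | 4:1 | 5 | 1/5 = 0.200 |
| 5 | 3:2 | 10 | 1/10 = 0.100 |
| 6 | 5:1 | 6 | 1/6 = 0.167 |
| 6 | 4:2 | 15 | 1/15 = 0.067 |
| 6 | 3:3 | 20 | 2/20 = 0.100 |
| 7 | 6:1 | 7 | 1/7 = 0.143 |
| 7 | 5:2 | 21 | 1/21 = 0.048 |
| 7 | 4:3 | 35 | 1/35 = 0.029 |

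No split of five or six estimates reaches 0.05. When one level holds a single estimate, the floor is 1/n, so 20 estimates are needed (1/20 = 0.05). Defining p as twice the smaller tail would not lower any of these floors.

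**Check by enumeration.** Random-effects meta-regression with every labelling enumerated, 200 simulated data sets per split and a very large effect (difference in log RR of −1.2), gave 0% power at every split of five and six. The same effect gave 95% to 100% at seven with 5:2 or 4:3 splits, and 0% at 6:1.

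**Beyond the floor.** For a true VE of 30% versus 60% (between-site SD of log OR 0.2, site SE 0.15 to 0.40; both assumed), two sets of simulations put power at 26% to 35% with seven estimates, 34% to 38% with eight and 52% to 55% with nine. Non-significance therefore remains weak evidence after the floor has been cleared.

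**Illustration with the SAP's artificial data.** The forest plot in section 3.4.7 gives counts by setting. As a code check, the hospital stratum reproduces exactly: 75.57% (66.01 to 82.45), I² 0%. Now take six estimates: primary care E, C and A, and hospital F, E and A.

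- Primary care: VE 47.9% (32.7 to 59.6), I² 0%
- Hospital: VE 75.6% (66.0 to 82.4), I² 0%
- Ratio of RRs, hospital to primary care: exp(−1.410 + 0.651) = 0.47 (95% CI 0.31 to 0.71), Wald p = 0.0004
- Permutation: of the 20 labellings, only the observed one and its mirror image reach the observed absolute statistic, so p = 2/20 = 0.10
- Pooled across setting: VE 62.6% (46.7 to 73.8), I² 65%

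Section 3.4.5 would describe setting as an unlikely source of heterogeneity here, although the two strata are clearly separated and the pooled figure describes neither. The subset was chosen to illustrate the point. The floor itself holds for any data.

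**The case against.** Several points on the other side are sound and limit the claim.

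- **The rule is permissive.** A reader might infer that the SAP would automatically merge settings or designs. It does not say so: meta-regression might be used, and pooling might be considered. Stratified analyses are offered in the same section, the forest plot shows every site, and the illustrative plot pools primary care and hospital separately.
- **I² is also cited.** A reader might infer that nothing but this p-value stands before pooling. Section 3.4.1 also points to the I² section. In the VE 30% versus 60% scenario, overall I² was at least 50% in 65% to 69% of simulated sets with five or six estimates, and at least 75% in 23% to 27%. That is a partial safeguard, and the SAP attaches no pooling threshold to it.
- **The significance level is an assumption.** A reader might infer that no difference can ever be significant with five or six estimates. At 0.10, the 3:2, 4:2 and 3:3 splits can reach significance. A one-sided 3:3 test reaches exactly 0.05.
- **Not every characteristic has this floor.** It does not apply to continuous characteristics, some multi-level ones, or models in which several covariates are permuted jointly. With two binary covariates permuted jointly, p reached 0.017 at five estimates and 0.011 at six. The SAP does not describe its permutation scheme.
- **The document is guidance**, to be updated after the pilot season, and the section is exploratory.

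None of this rescues the sentence that turns non-significance into an unlikely source of heterogeneity. It carries no qualification, and it is the stated ground for considering pooling.

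**Conclusion.** The inference in section 3.4.5 is wrong as written and should be corrected. The criticism of reading non-significance as absence of an effect holds at any number of estimates. The stronger statement, that the test cannot be significant and so always leaves pooling permitted, holds for five or six estimates, a single two-level characteristic and an assumed two-sided level of 0.05. The floors are then 0.10 to 0.20 and 0.067 to 0.167. Seven estimates with at least two in the smaller level are the minimum at which the test can be significant. The documents do not support going further and saying that strata will be merged automatically, or that all characteristics are affected. Since pooling is discretionary and stratum estimates remain visible, this is a should-fix rather than a fatal flaw.

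**What to change.** In section 3.4.5:

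1. Delete the sentence that infers an unlikely source of heterogeneity from a non-significant result.
2. Report estimates by stratum, with the ratio of pooled RRs or ORs between strata and its 95% CI.
3. State the significance level and sidedness of the permutation test. Do not use its p-value for a two-level characteristic when the number of distinct labellings makes p ≤ 0.05 unattainable.
4. Present any figure pooled across the characteristic only beside the stratum estimates, and without a claim of homogeneity.

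An equivalence rule, such as pooling only if the CI of the ratio lies within 0.80 to 1.25, is tempting but is not recommended. In simulations with truly identical strata and the site-level inputs above, it was met in 0% of sets at 5, 7 and 10 estimates, under 1% at 20 and 18% at 40. It would replace a test that cannot reject with a criterion that is almost never met.

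The change is to wording only. The cost is fewer stand-alone cross-stratum figures and wider stratum-specific intervals.
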